**Data analysis:**

Unless otherwise specified, the following pertains to the entire study (Study Parts One and Two).

Long-term safety will be assessed based on adverse events (AEs), laboratory and vital signs as well as other investigations performed when clinically indicated. Analysis of the safety variables will be conducted on the safety set.

Incident rates (IRs) of adverse events per 100 patient-years will be summarized by highest assigned fingolimod dose (fingolimod 0.5 mg/day and any dose of fingolimod).

To further evaluate the risk with longer fingolimod exposure duration, IR if adverse events reported with different fingolimod exposure durations will be compared.

In addition, the incidence of adverse events (new or worsened from the long-term extension baseline) reported during the long-term extension will be summarized by primary system organ class and preferred term as frequency count and percentage of patients with adverse events.

The incidence of death, serious adverse events (SAEs), AEs leading to discontinuation, and other significant AEs will be summarized separately by primary system organ class and preferred term.

Laboratory data will be summarized using summary statistics of raw data and change from baseline values. For liver function tests, the frequencies and percentages of patients with elevations of 1, 2, 3, 5, and 10 times upper limit of normal will be summarized by visit (Study Part One only).

Vital sign data will be summarized as descriptive statistics for change from baseline value. The incidence rates of notable vital sign abnormalities will be summarized.

Summary statistics for ECG parameters (including pre-dose ECG for patients who have this evaluation done) will be summarized by visit. Incidence of abnormal ECGs by type of abnormality will be presented.

The incidence of macular edema events will be summarized as frequency distributions. The patient data listing will also be provided.

Pulmonary function test data (FEV1, FVC, and DLCO, percentage of predicted value for these three variables, and smoking status) will be summarized.

The skin assessment will be summarized based on abnormal findings.

The safety data will also be summarized by subgroups for the supportive safety analysis purpose.

The safety data obtained after discontinuation of the study drug will be summarized.

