6.1 Duration of exposure

The duration of exposure to fingolimod study drug will be defined as the number of days from first dose date of fingolimod among all studies to last dose date of the long-term follow-up study part I, excluding the days for which the patient did not take fingolimod (i.e., periods of temporary interruption). The number and percentage of patients being exposed for a minimum of ≥ 1 day, ≥ 90 days, ≥ 180 days, ≥ 360 days, etc. will be presented. Summary statistics of duration of exposure will also be provided. Patient-years of exposure will be reported and is calculated as the (sum of the total number of days on fingolimod study drug for all patients in the treatment group)/365.25. The above summaries will be presented for the fingolimod safety set and the subgroup of fingolimod safety set patients from Phase II/III studies.

Similar summaries will be provided for the duration of exposure to fingolimod study drug during the long-term follow-up study part I, which is defined as the number of days from first dose date of fingolimod in the long-term follow-up study to the last dose date, excluding the days for which the patient did not take fingolimod. Duration of exposure to fingolimod study drug during the long-term follow-up study part I will be presented for the safety set.

The fingolimod dose administration records during the long-term follow-up study part I will be listed for the safety set.

7 Concomitant medication

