8.1.2 Annualized relapse rates

Annualized relapse rate (ARR) is defined as the *number of relapses* experienced during a specific period of time adjusted to a one-year period. The ‘number of relapses’ can refer to

either the number of *confirmed relapses* or the number of *all relapses* (including both confirmed and unconfirmed relapses).

Confirmation of relapses is not collected in the following studies: CFTY720D2316, CFTY720D2320, CTY720D2399E1, and the long-term follow-up study prior to protocol amendment 4. Therefore, the number of confirmed relapses during this time is not able to be reported. Additionally, confirmed relapses will not be reported for patients from the CFTY720D2324 study since it is a phase IIIb study and confirmation is not collected in the long-term follow-up study for patients coming from previous studies that are not phase II/III. The number of unconfirmed relapses is also not able to be reported for study CTY720D2399E1 since the study does not collect relapse start dates. However, note that the time during which number of relapses is not able to be counted and the time off study for patients who re-enrolled into the long-term follow-up study will still be included in the time in study, which can make the ARR appear lower than it actually is. If confirmation of a relapse is missing or not collected, the relapse will be treated as an unconfirmed relapse. Therefore, ARR based on all relapses (confirmed or unconfirmed) should be considered a more reliable estimation of relapse rate than ARR based on confirmed relapse.

The group level (aggregate) ARR will be calculated as follows: (total number of relapses) / (total number of days in the study for all patients for that specific period of time) x 365.25.

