9.1.2.2 Adverse events during the fingolimod treatment period

Unless otherwise specified, all non-serious adverse events with onset on or after first dose date of fingolimod among all studies to last dose date of fingolimod + 45 days are included. All serious adverse events (SAEs) with onset on or after the first dose date of fingolimod among all studies are also included in the summaries. Also, unless otherwise specified, adverse events will be summarized for the fingolimod safety set, by primary system organ class and preferred term, and will show the number of patients with at least one adverse event and the incidence rate of adverse events per 100 patient-years in each SOC or PT category.

The AE incidence rate (IR) is calculated per 100 patient-years. IR is defined as: the number of patients experiencing at least one event in a particular category, over the total patient-years of the “at risk” population for that event multiplied by 100. An underlying Poisson process for incidence rate within treatment group is assumed.

To calculate the total patient-years (time at risk) of the “at risk” population:

1. For patients who have a particular AE category, sum the number of days from first dose date of fingolimod among all studies to the first occurrence of that particular AE category

2. For patients who did not have a particular AE category, sum the number of days from first dose date of fingolimod among all studies to last dose date of fingolimod + 45 days.
3. Add the time at risk for patients who had a particular AE category with the time at risk for patients who did NOT have a particular AE category. This is the total time at risk of that AE category.
4. Divide the total time at risk by 365.25.

Incidence rate of adverse events will be presented for the fingolimod safety set and for the subgroup of fingolimod safety set patients from phase II/III studies, by SOC and PT. Incidence rate of AEs, excluding AE listed in the core data sheet, will be presented by PT. Incidence rate of AEs that fulfill the risk search term (defined in the case retrieval sheet) will be presented by risk name and lower level terms. Similarly, all above indicated AE IR summaries will be conducted for SAEs.

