To further evaluate the long-term AE rate (based on patient count and percentage) within a particular fingolimod treatment duration, an analysis based on yearly intervals since first dose of fingolimod will be conducted. For summaries on this set of patients, all AEs and SAEs with onset on or after first dose date of fingolimod (among all studies) to last dose date of fingolimod are included. Each yearly interval will contain 360 days. For example: Year 1 will consist of Day 1 to Day 360, Year 2 will consist of Day 361 to Day 720, Year 3 will consist of Day 721 to Day 1080, Year 4 will consist of Day 1081 to Day 1440, Year 5 will consist of Day 1441 to Day 1800, and so on. Patients will be summarized within a particular yearly interval if they have been receiving study treatment for at least one day in that particular interval. The number and percentage of these patients who have adverse events with onset date occurring during the interval will be summarized. For example, for the Year 1 group, patients with at least one day exposure to fingolimod will be included, and AEs with onset date occurring between Day 1 and Day 360 will be summarized. For the Year 2 group, patients with at least 361 days exposure to fingolimod will be included, and AEs with onset date occurring between Day 361 and Day 720 will be summarized. The same will be done for other intervals.

Adverse events summarized by year will include the following:

- Adverse events, by yearly interval, primary system organ class, and preferred term
- Serious adverse events, by yearly interval, primary system organ class, and preferred term
- Adverse events that fulfill the risk search term, by yearly interval
- Serious adverse events that fulfill the risk search term, by yearly interval

Intervals will be included based on the length of fingolimod exposure. Risk search terms are defined in Novartis' case retrieval sheet. Associated summaries will be presented by risk name and lower level terms.

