To further evaluate the disposition within a particular fingolimod treatment duration, study completion and discontinuation will be summarized in separate tables based on patients' fingolimod exposure by cumulative yearly interval. Patients will be summarized within a particular yearly interval if they have been receiving study treatment for at least one day in that particular interval. For example: year 1 will consist of subjects on fingolimod treatment for at least 1 day; year 2 will consist of subjects on fingolimod treatment for at least 361 days, year 3 will consist of subjects on fingolimod treatment for at least 721 days and so on. For study completion, the number and percentage of patients who completed the study part 2, and who move to commercial fingolimod after study completion will be provided by yearly exposure group as defined above. For study discontinuation, the number and percentage of patients who discontinued the study part 2, along with the reason for discontinuation, and who move to commercial fingolimod after study discontinuation will be provided by yearly exposure group as defined above.

The patients who discontinued from the study part 2 and corresponding reasons will be listed for the enrolled set. Additionally, a similar listing will be provided for the enrolled set of patients from D2312 and D2402 studies who discontinued early from the study part 2.

5 Background and demographic characteristics

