9.1.2.1.2 Incidence rate of adverse events

The AE incidence rate (IR) is calculated per 100 patient-years. IR is defined as: the number of patients experiencing at least one event in a particular category, over the total patient-years of the “at risk” population for that event multiplied by 100. An underlying Poisson process for incidence rate within treatment group is assumed. For the summary time period for extension part 2, only AEs with a start date between first dose date of fingolimod during the study part 2 and the last dose date of fingolimod + 45 days will be counted; or SAEs with a start date on or after first dose date of fingolimod during the study part 2 will be counted.

To calculate the total patient-years (time at risk) of the “at risk” population:

1. For patients who have a particular AE category, sum the number of days from first dose date of fingolimod during the study part 2 to the first occurrence of that particular AE category
2. For patients who did not have a particular AE category, sum the number of days from first dose date of fingolimod during the study part 2 to last dose date of fingolimod + 45 days.
3. Add the time at risk for patients who had a particular AE category with the time at risk for patients who did NOT have a particular AE category. This is the total time at risk of that AE category.
4. Divide the total time at risk by 365.25.

Incidence rate of adverse events will be presented for the safety set. Incidence rate of AEs, AEs by relationship, excluding AE listed in the core data sheet, will be presented by PT. Similarly, all above indicated AE IR summaries will be conducted for SAEs.

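### The by-year adverse event tables in both SAPs lack interval patient-years: percentages understate on-treatment risk where patients leave mid-interval for unrelated reasons, and the synopsis comparison of incidence rates by exposure duration is not produced

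*SAP*

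**What the plan says.** Section 9.1.2.2 of the SAP for Part I and section 9.1.2.2 of the SAP for Part 2 set up the by-year tables in the same way. Time since first fingolimod dose is cut into 360-day intervals. The metric is patient count and percentage. Patients belong to an interval "if they have been receiving study treatment for at least one day in that particular interval", and only onsets up to last dose are counted. The example that follows words membership differently: "For the Year 2 group, patients with at least 361 days exposure to fingolimod will be included".

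Incidence rates per 100 patient-years exist, but only pooled over time:

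- **Part I, 9.1.2.2:** for patients without the event, time at risk is "the number of days from first dose date of fingolimod among all studies to last dose date of fingolimod + 45 days". Rates are given for the fingolimod safety set and its phase II/III subgroup.
- **Part 2, 9.1.2.1.2:** for patients without the event, the instruction is to "sum the number of days from first dose date of fingolimod during the study part 2 to last dose date" plus 45 days, so the rate covers Part 2 only.

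The protocol is not uniform on what is wanted. The synopsis (Data analysis) states: "IR if adverse events reported with different fingolimod exposure durations will be compared". Section 9.4.1.1 says only that events at different exposure durations will be assessed. Section 9 says exposure-adjusted incidence is used to look at risk over time, without requiring a split by year.

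**The concern.** A patient treated for one day of an interval weighs as much in the denominator as one treated for all 360, yet has had almost no time in which an event could be counted. Any interval with many partial contributors therefore shows a percentage below the risk that patients on treatment actually face.

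Long-term safety is the primary objective, and Protocol 1.1 says more data are needed on rare or time-dependent events. The tables in 9.1.2.2 are the only adverse event tables by treatment year. A modest rise in risk in a partly observed interval could be masked, and the rate comparison that would guard against this is mentioned in the synopsis but specified in neither SAP.

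**Working it through.** The documents state no adverse event rate, no exit share and no sample size calculation, so there is no figure of the plan's own to reproduce. The following is illustrative.

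**Inputs**
- Interval length: 360 days (9.1.2.2, both SAPs), so y = 360/365.25 = 0.9856 years.
- First-event hazard L: assumed 5 per 100 patient-years and constant, in line with the Poisson process both SAPs assume.
- Share f leaving during the interval: assumed 10%, 30% or 50%, evenly spread in time and unrelated to the event.

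**Formulas**
- Full-interval risk = 1 − exp(−Ly) = 1 − exp(−0.0493) = 4.81%.
- Risk counted in a leaver = 1 − (1 − exp(−Ly))/(Ly) = 1 − 0.04809/0.04928 = 2.42%.
- Table percentage = (1 − f) × 4.81% + f × 2.42%.

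| f | Table shows | Shortfall against 4.81% | True rise hidden against a fully observed year |
|---|---|---|---|
| 10% | 4.57% | 5% | 5% |
| 30% | 4.09% | 15% | 18% |
| 50% | 3.62% | 25% | 34% |

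The shortfall is close to f/2 because an average leaver is observed for half the interval. It barely depends on the event rate: at f = 50% it stays between 24% and 25% for hazards from 0.5 to 20 per 100 patient-years. As a check at 10 per 100 patient-years and f = 50%, the formula gives 7.08% against a full risk of 9.39%, and a simulation of 2,000,000 patients gives 7.10%. If the event itself is the only reason for leaving, there is no shortfall (simulated 9.35% against 9.39%).

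**With interval person-time.** At f = 50% and L = 5 per 100, stayers contribute 0.04809/0.05 = 0.962 years and leavers 0.02424/0.05 = 0.485 years, a mean of 0.723. The rate is 100 × 0.03616/0.723 = 5.0, the assumed value. The same holds at every f.

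**What a reader could do without the fix.** Consecutive denominators give f roughly, and dividing by (1 − f/2) returns 4.81% to 4.82% under even exit. It fails if exits bunch. With f = 50% and all exits at one quarter of the interval, the table shows 3.02% and the corrected value is 3.02/0.75 = 4.02%, 16% too low. At three quarters it shows 4.22% and corrects to 5.63%, 17% too high.

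**Membership.** Part I section 6.1 defines exposure as "excluding the days for which the patient did not take fingolimod". Take a patient interrupted for 30 days in Year 1 with last dose on Day 380. That patient is treated in Year 2 but has 380 − 30 = 350 exposure days, so the stated rule includes the patient and a literal reading of the example does not.

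**The case against.** The strongest reply is that the tables are openly descriptive. Section 9.1.2.2 declares its metric, Protocol 9.4.1 plans no inference, and Protocol 9.4.1.1, the operative section, asks only for an assessment, which the tables provide. On that view the gap is a mismatch between the synopsis and the body of the protocol. This stands in part: the synopsis line is the only place that promises a comparison of rates.

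It is also fair that other outputs help. The Part I exposure table (6.1) has cut-points at 90, 180 and 360 days and onwards, which allows a crude estimate of interval person-time. In Part 2, section 4, "study completion and discontinuation will be summarized in separate tables" by yearly exposure. The Part 2 incidence rate covers late exposure for patients continuing from Part One. None of these is event-specific within an interval, and none gives a comparison year by year.

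A reader might go further and infer that the tables conceal a rising late risk, or that the bias concentrates in the close-out years. The documents do not support either. Close-out follows a calendar date or 60 months in this study (Part I SAP, section 1), whereas the intervals run from first fingolimod dose in any study, so exits may spread over many exposure years. Early-year data are also selected. The analysis sets (2.5, both SAPs) contain only patients who later entered the long-term study or Part 2, and Protocol 4.2 excludes those who permanently stopped a fingolimod study for an adverse event.

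The membership wording and the 360-day against 361-day cut-offs are small matters: the main rule is explicit, and the cut-offs differ only for patients at the boundary day.

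**Conclusion.** The point holds in a conditional form and is worth fixing. Where patients leave mid-interval for reasons unrelated to the event, the by-year percentage understates the full-interval on-treatment risk by about f/2 under even exit. This is bound to matter in each patient group's last, partly observed intervals. Its size in any given exposure year is unknown, because neither the exit shares nor their timing is documented; the 5%, 15% and 25% figures rest on assumed f and even, non-informative exit.

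The synopsis comparison of incidence rates by exposure duration is not delivered by either SAP, although Protocol 9.4.1.1 requires less. The net direction of any distortion across years is not established, so neither the percentages nor an interval rate alone can show a time effect.

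**What to change.** In section 9.1.2.2 of both SAPs:

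- Keep the number and percentage. For each interval add patient-years at risk (to first event in the interval, last dose or interval end, divided by 365.25) and the incidence rate per 100 patient-years, with a 95% CI under the Poisson assumption already stated. Do this at least for any adverse event, serious adverse events and the risk search terms.
- Define membership only by at least one treated day in the interval, counted by study day since first fingolimod dose.
- State how off-drug gaps are handled, the same way in numerator and person-time. Part I section 8.1.2 already concedes for the relapse rate that uncounted time and time off study left in the denominator "which can make the ARR appear lower than it actually is". Here, if 10% of patients were off drug for half an interval and no gap events were counted, a rate of 5 would read about 5 × (1 − 0.1 × 0.5) = 4.75.
- Footnote that the interval rate will not reconcile with the pooled rate, which uses first event ever and last dose + 45 days.
- Footnote that early-year data include only patients who later entered the long-term study or Part 2, so a rise from early to late years must not be read as a time effect on the rate alone.
- Reconcile the synopsis with Protocol 9.4.1.1. As a minor clean-up, align the 360-day cut-offs in Part I section 2.5.1 with the 361-day ones in Part I 9.1.2.2 and Part 2 section 2.5.1.

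The dates needed are already collected. Person-time is event-specific, so the programming is modest but must be repeated by event category, interval and dose group. Later-year figures may look less favourable, and without the footnote readers would see two rates that do not match.

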## 6.2 Previous Study Details

In order to collect accurate information about the patient's previous fingolimod study details, the following records will be collected at the enrollment visit for each patient: the patient's previous fingolimod study number, center number, and patient number.

Upon the implementation of Amendment 4, the following information will be collected: the date of full approval for Amendment 4, whether or not the patient is re-enrolling into this study (defined as a patient who previously completed CFTY720D2399 based on the original study endpoint who is now re-entering the study using the originally assigned patient ID number) and the date of re-enrollment. In addition, data will be collected on any potential treatment gap during the time a patient may have temporarily been out of a fingolimod study and whether or not the patient went onto commercially available medication during the gap, if applicable.

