2.3.2 Study day

The day of first administration of fingolimod study drug is defined as *Day 1*. Day 1 does not need to occur in the long-term follow-up study.

All other study days will be labeled relative to Day 1. Thus, study day for a particular event date on or after Day 1 is calculated as: (*Date of event – Date of first dose of fingolimod study drug + 1*). An event that occurs prior to Day 1 is calculated as: (*Date of event – Date of first dose of fingolimod study drug*).

In addition to calculating study day with respect to the first dose date of fingolimod drug across all studies, study day will also be calculated relative to the first dose date of fingolimod during the long-term follow-up study.

The number of days after permanent study drug discontinuation will be calculated as (*Date of event – Date of last dose of fingolimod study drug*).

The duration of an event will be calculated as (*Event end date – Event start date + 1*). Day 0 will not be used.

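### The yearly adverse-event tables place events by calendar study day but give two entry rules that conflict for patients with treatment gaps, and one of them can drop a treated late interval

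*SAP*

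**What the plan says.** Events are placed on a calendar clock. In Part I section 2.3.2, "The day of first administration of fingolimod study drug is defined as" Day 1, and later days are numbered from it without removing interruptions. In 9.1.2.2, "Each yearly interval will contain 360 days" and, for instance, "Year 2 will consist of Day 361 to Day 720". Onsets from the first to the last fingolimod dose are counted.

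For who belongs in each column, the same section gives two rules:

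- General sentence: patients are summarised in an interval "if they have been receiving study treatment for at least one day in that particular interval".
- Worked example: "For the Year 2 group, patients with at least 361 days exposure to fingolimod will be included". The other intervals are to be handled alike.

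It closes with "Intervals will be included based on the length of fingolimod exposure". It does not say which rule governs, and it does not refer to a definition of exposure. Part I section 6.1 defines duration of exposure from the first fingolimod dose in any study, "excluding the days for which the patient did not take fingolimod (i.e., periods of temporary interruption"). Part 2 section 6.1 removes interruptions in the same way, but defines exposure during Part 2 only.

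Section 2.5.1 adds duration-of-treatment subgroups. Part I sets the Year 2 threshold at 360 days and Part 2 at 361. Part 2 section 4 (disposition) repeats the pattern of a treated-day rule followed by a day-count example, and Part 2 section 9.1.2.2 repeats the Part I text.

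**The concern.** For a patient treated without interruption the two rules agree. For a patient with a gap, net exposure runs behind the calendar, so a net-exposure threshold combined with calendar placement of events mixes two clocks. A programmer who follows the example, the closing line and 6.1 would build a different membership flag from one who follows the general sentence.

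The tables matter because Protocol 9.4.1.1 calls for adverse events to be assessed by length of fingolimod exposure, and these tables deliver that. In Part 2 they are the only adverse-event summary under the fingolimod treatment period; the Part 2 incidence rates start at the first Part 2 dose. What the exposure rule can drop is the latest treated interval.

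The protocol foresees gaps. Antibody-negative patients who choose varicella vaccination stop for 2 months before it and 1 month after (6.5.4.2). With the protocol's 30-day month that is 90 days. Patients may restart after pregnancy and nursing (6.5.8, no length given). For re-enrolling patients, "data will be collected on any potential treatment gap during the time a patient may have temporarily been out of a fingolimod study" (6.2).

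**Working it through.** **Inputs.** Interval length 360 days, the interval limits and both entry rules: 9.1.2.2. Day 1: 2.3.2. Net exposure: Part I 6.1.

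**The plan's own limits.** Interval N runs from Day 360(N−1)+1 to Day 360N. This gives starts of 1, 361, 721, 1081 and 1441, as printed in 9.1.2.2. Part I 2.5.1 uses 360(N−1), that is 360, 720, 1080 and 1440, one day lower.

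**When the exposure rule loses the last treated interval.** Let the last dose fall on day r (1 to 360) of interval K, with G off-drug days before it.

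- Last-dose day = 360(K−1) + r.
- Net exposure = 360(K−1) + r − G.
- Entry to interval K needs net exposure of at least 360(K−1) + 1, that is r − G ≥ 1.
- So interval K is lost if and only if r ≤ G.

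**One patient.** Treated Days 1–700, off Days 701–1059 (359 days), treated Days 1060–2000.

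- Net exposure = 700 + (2000 − 1060 + 1) = 700 + 941 = 1641.
- Year 5 needs 1441 (met); Year 6 needs 1801 (not met).
- Check: r = 2000 − 1800 = 200, and 200 ≤ 359.
- A serious event on Day 1950, on drug in calendar Year 6 (Days 1801–2160), is in no yearly column under the exposure rule. It is in Year 6 under the general sentence.

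**Other dosing patterns.**

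| Pattern (days) | Net | Last dose | General rule | Net-exposure rule |
|---|---|---|---|---|
| 600 on | 600 | 600 | Years 1, 2 | Years 1, 2 |
| 200 on, 300 off, 100 on | 300 | 600 | 1, 2 | 1 (loses 2) |
| 300 on, 200 off, 100 on | 400 | 600 | 1, 2 | 1, 2 |
| 1000 on, 60 off, on to Day 1470 | 1410 | 1470 | 1–5 | 1–4 (loses 5) |
| 1000 on, 60 off, on to Day 1700 | 1640 | 1700 | 1–5 | 1–5 |
| 360 on, 360 off, 400 on | 760 | 1120 | 1, 3, 4 | 1, 2, 3 (loses 4, fills 2 with no treated day) |
| 500 on, 540 off, 500 on | 1000 | 1540 | 1–5 | 1–3 (loses 4 and 5) |

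**Share losing the last interval.** If r is uniform on 1 to 360, the share is min(1, G/360): 4.2% at 15 off-drug days, 8.3% at 30, 16.7% at 60, 25% at 90, 50% at 180, and 100% at 360 or more.

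**When a wholly off-drug interval is filled.** One gap must cover a full 360-day interval, which is impossible at 359 days or fewer. For a single gap of G days from 360 to 719, with a uniform start, the share of positions covering an interval is (G − 359)/360: 0.3% at 360, 25% at 450 (91/360), 50% at 540 (181/360) and 100% at 719. Enough later treatment is also needed to pass the net threshold.

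**The case against.** The strongest reply is that the general sentence is the operative rule and the 361-day sentence only illustrates it for continuous treatment, where the two agree. Section 9.1.2.2 does not cite 6.1, whose definition serves the exposure tables, and the 2.5.1 subgroups do not say that interruptions are removed. The closing line may only say which columns are shown. If exposure meant elapsed time from first to last dose, no treated interval would be lost, although a wholly off-drug one could still be filled. This much stands: a reader might infer that net exposure is the plan's settled rule, and the documents do not support that. They contain an unresolved conflict.

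Other limits also stand:

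- A reader might infer that every patient with a gap loses the last treated year. At 90 off-drug days, 75% lose nothing under the uniform assumption.
- In the one-patient example, Year 3 holds only 21 treated days (1060–1080). That membership arises under the general sentence too, so it is not a product of the conflict.
- A re-enrolment gap need not be off drug: Protocol 6.2 also records whether commercial medication was taken in it. The vaccination gap applies only to a minority by choice, and no length is given for a pregnancy gap.
- A reader might infer that late risks are hidden. A dropped patient leaves both numerator and denominator, so the direction of bias in the yearly percentages cannot be known. The Day 1950 event still falls within the scope of the Part I incidence rates and, if recorded in this study's database, of the Part I summaries and listings.
- The analyses are descriptive (Protocol 9.4.1), and the 360 versus 361 difference is one day.

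What the reply does not remove is that a stated example, the closing line and the subgroup definitions all point to duration, while events are placed by calendar day.

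**Conclusion.** The conflict between the two entry rules is real and appears in both SAPs. Under the exposure rule, with exposure taken net as in Part I 6.1, a patient loses the last treated interval exactly when total off-drug days reach or exceed the days into it. The 25% and 100% figures are shares of patients with that much off-drug time, not of the study population, and they rest on a uniform last-dose day. The number and length of gaps are not stated, so the overall effect cannot be sized. The point is of low to moderate importance: it leaves open which patients and events enter the late columns of the plan's main look at risk by duration, but it does not remove events from the report.

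**What to change.** In 9.1.2.2 of both SAPs, state that the general sentence governs: a patient is in Year N if at least one fingolimod dose was taken on a study day from 360(N−1)+1 to 360N. Reword the 361-day examples and the closing line on which intervals are included to match. Align the duration subgroups used for these tables in 2.5.1 of both plans (including 360 against 361 in Part I) and the day-count examples in Part 2 section 4.

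In every pattern tabulated above, this rule loses no treated interval and fills no wholly off-drug one. One consequence should be stated: onsets in an interval with no treated day will then be outside the yearly tables.

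The cost is SAP wording and one membership flag derived from dosing records already collected (Protocol 6.3). No new data are needed.
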